Retrospective Evaluation of Prosthetic Complications and Peri-implant Bone Resorption in Implant-Supported Single Unit Fixed Restorations

Study Protocol

Date: 07.04.2023

Department of Prosthetic Dentistry

Afyonkarahisar Health Sciences University, Faculty of Dentistry

Pre-assignment Details

Participants included in the study were later excluded from the analysis due to reasons such as missing data in patient records, the presence of data outside the specified time frame, patients initially thought to meet the study criteria being incorrectly coded, or medical records being in an unsuitable format or unreadable.

Arm/Group Information

This study does not include any specific study or control groups. The research focuses on the follow-up of participants with certain characteristics over a specified time period.

Type of Units Assigned

- **Period(s):** This is a retrospective study following a 12-month period.
Period Title: Overall Study
Started: This study was conducted by including patients 12 months after delivery of the implant-supported restoration. The sample was completed when a total of 100 patients were reached.
Completed: The number of participants at the end of the study is 100.

Baseline Characteristics

- **Arm/Group Information:** There were no separate groups in the study. The study included a 12-month follow-up of participants with implant-supported single-unit restorations.
Arm/Group Title: There were no separate groups in the study.
- **Baseline Analysis Population Information**
Overall Number of Baseline Participants: 100 participants
- **Baseline Measure Information**
Baseline Measure Title
Age: Age, Continuous
Sex/Gender: Female, Male
- **Measure Type:** Count of Participants

- **Measure of Dispersion:** Not Applicable
- **Baseline Measure Data: Not Available.** The study does not have any baseline data, because the data in the study only includes data from participants at the end of the 12-month follow-up.
- **Unit of Measure:** Not Available

Outcome Measures:

- **Outcome Measure Information:** Implant survival and prosthetic complication rate
 - Outcome Measure Type:** Primary
 - Outcome Measure Title:** Implant survival and prosthetic complication rate
 - Outcome Measure Time Frame:** 12 months after delivery of implant-supported restoration
 - Arm/Group Information:** There were no separate groups in the study. The study included a 12-month follow-up of participants with implant-supported single-unit restorations.

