Analysis Population Information:

Overall Number of Participants Analyzed: 100 participants

Outcome Measure Data Table

Measure Type: Count of Participants

Measure of Dispersion/Precision: Not Applicable

Outcome Measure Data: The effect of prosthetic, anatomical and surgical parameters on implant survival rate and prosthetic complications

Unit of Measure: Implant survival and prosthetic complications rate

Statistical Test of Hypothesis:

P-Value: p<0.05

Method: Chi-Squared

Adverse Event Information: Since this is a retrospective analysis, adverse events were not evaluated.

Certain Agreements:

- **Are all PIs Employees of Sponsor?** Yes: The principal investigator is an employee of the sponsor

Results Point of Contact:

- **Name or Official Title:** [name]. Assistant Professor at Afyonkarahisar Health Sciences University, Department of Prosthodontics.
- **Organization Name:** Afyonkarahisar Health Sciences University
- **[contact]
- **E-mail:** [contact]

Document Upload Information:

- **Document Type:** Study Protocol with Statistical Analysis Plan (SAP)
- **Document Date:** 07.04.2023

This retrospective study included 100 volunteer patients aged between 30 and 77 who presented at the Department of Prosthetic Dentistry at Afyonkarahisar Health Sciences University Faculty of Dentistry for prosthetic treatment and received a single-unit implant-supported crown. The evaluation of the included patients was conducted during their 12-month follow-up control appointments after prosthetic loading. After obtaining oral and written consent from the patients, demographic data, prosthetic complications related to single-unit fixed implant-supported prostheses, and peri-implant bone loss assessed via radiographic controls were recorded and analyzed. During clinical examinations, the compatibility of the prostheses with adjacent teeth and gingiva, the presence of gingival recession, patient complaints about the prosthesis, and any prosthetic complications were assessed and recorded. Statistical analyses were performed retrospectively after evaluating the collected data.

Ethical Approval for the Study

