Since participation in this study was voluntary and conducted with volunteers, it was reviewed by the Clinical Research Ethics Committee of Afyonkarahisar Health Sciences University. The study was unanimously deemed to comply with medical ethical standards (Date: 07.04.2023, Protocol Code: 2023/4). All volunteers signed an informed consent form approved by the ethics committee before participating in the study.

Volunteer Selection

This study included 100 volunteer patients who applied to the Department of Prosthetic Dentistry at Afyonkarahisar Health Sciences University Faculty of Dentistry for prosthetic treatment and received a single-unit implant-supported crown. Patients were selected from archives and evaluated during their 12-month follow-up appointments through clinical and radiographic examinations. To determine the number of volunteers needed for the study, a sample size calculation was performed using *GPower software* (*GPower* Ver. 3.0.10, Franz Faul, University of Kiel, Germany). With a significance level of $\alpha=0.05$ (95% confidence interval), an effect size (d) of 0.5, and power ($1-\beta$) = 0.80, at least 80 patients were required. To account for potential dropout and data loss during follow-up, an additional 25% (20) patients were added, resulting in 100 patients at the start of the study.

Systemic and dental anamneses of the volunteers were thoroughly evaluated, and inclusion and exclusion criteria were established. Patients meeting the inclusion criteria were provided detailed information about the study plan before the start. Those who agreed to participate signed the

Inclusion Criteria

1. Patients who had received single-unit dental implant treatment and had 12 months elapsed since prosthetic loading.
2. Patients aged 18 and older, regardless of gender.
3. Patients with no systemic health issues.
4. Non-smokers.
5. Patients for whom radiographic bone loss, mobility, and prosthetic complications data were recorded and evaluated.
6. Patients who signed the informed consent form voluntarily after being fully informed about the study's purpose, duration, and requirements.

Exclusion Criteria

1. Patients diagnosed with osteoporosis and/or undergoing bisphosphonate treatment during or after treatment.
2. Patients with uncontrolled systemic diseases (e.g., diabetes mellitus, heart diseases, liver diseases).
3. Patients with a history of head or neck radiotherapy.
4. Patients on chronic medication (e.g., steroids, antidepressants).

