5. Smokers.
6. Patients without radiographs immediately after prosthetic loading.
7. Patients with psychiatric problems.
8. Patients with missing data on radiographic bone loss, mobility, prosthetic complications, or implant dimensions.
9. Patients with short implant designs.
10. Patients who lost implants before the 12-month follow-up.

Data Collection

The evaluations conducted during the patients' 12-month follow-up appointments were recorded and analyzed. The parameters assessed during these appointments include:

A. Demographic Data

1. Age of the patient.
2. Gender of the patient (Male/Female).
3. Education level (Primary School, Secondary School, High School, Undergraduate, Graduate).

B. Clinical Parameters

1. Tooth brushing habits (None, Once daily, Twice daily, More than twice daily).
2. Presence of functional pain (Yes/No).
3. Mobility (Yes/No).
4. Presence of exudate (Yes/No).
5. Attached gingiva (≥ 3 mm) (Yes/No).
6. Reason for tooth extraction (Endodontic, Periodontal, Other).
7. Immediate implant placement after extraction (Yes/No).
8. Implant diameter (Narrow < 3.75 mm, Standard ≥ 3.75 mm and < 5 mm, Wide ≥ 5 mm).
9. Implant length (Short implants excluded; Standard ≥ 10 mm).
10. Implant type by tissue relationship (Bone Level, Tissue Level).
11. Anatomical location of the implant (Maxillary Anterior/Posterior, Mandibular Anterior/Posterior).
12. Type of abutment (Standard, Screw-Retained, Ti-Base).
13. Status of the opposing arch (Natural Tooth, Tooth-Supported Fixed Prosthesis, Implant-Supported Fixed Prosthesis, Implant-Supported Removable Prosthesis, Tooth-Supported Removable Partial Prosthesis/Full Denture).
14. Occlusal table dimensions (Normal/Reduced by 30-40%).
15. Superstructure material (Metal-Ceramic, Monolithic Zirconia, Monolithic Glass Ceramic).
16. Presence and history of screw loosening (Yes/No).
17. Presence and history of cementation loss (Yes/No).
18. Framework-ceramic separation (Chipping) (Yes/No).

Data Evaluation

Evaluation of Implant Success and Survival

The success and survival of the implants were evaluated based on the 2007 consensus criteria established by the International Congress of Oral Implantologists (ICOI). The data were categorized

into four groups: Healthy-Successful, Sufficient Survival, Compromised Survival, and Unhealthy-Failed.

Evaluation of Radiographic Bone Loss

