Digital radiographs (periapical and panoramic films) taken at the end of prosthetic treatment and during the 12-month follow-up were analyzed using Planmeca Romexis® software (Planmeca, Helsinki, Finland). Marginal bone loss was measured using ImageJ software (ImageJ 1.54g, NIH, USA). Measurements were calibrated based on the actual implant length. The mesial and distal marginal bone loss was calculated separately by subtracting the values obtained immediately after prosthetic loading from those at the 12-month follow-up.

Statistical Analysis

The collected data were analyzed using SPSS Statistics V.26 (IBM SPSS Statistics, USA). The normality of parameters was assessed using the Kolmogorov-Smirnov and Shapiro-Wilk tests. Descriptive statistical methods (mean, standard deviation, median, frequency) were employed. Quantitative data and intergroup comparisons were evaluated using the Kruskal-Wallis test, with Dunn's test for post hoc analysis. The Mann-Whitney U test was used for pairwise comparisons, and the Fisher-Freeman-Halton Exact Chi-Square test was employed for qualitative data comparisons. A significance level of $p<0.05$ was considered statistically significant.

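### Implant survival at 12 months is a primary outcome, but patients who lost an implant before 12 months are excluded, so survival as implant in place is fixed at 100/100

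*Combined protocol and SAP*

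**What the plan says.** - **Outcome.** Under Outcome Measures, the single primary outcome is "Implant survival and prosthetic complication rate", timed at 12 months from delivery of the restoration. The Outcome Measure Data entry gives the intended inference: "The effect of prosthetic, anatomical and surgical parameters on implant survival rate and prosthetic complications". The test named there is chi-squared with p<0.05.
- **Eligibility.** Exclusion Criteria, item 10, removes "Patients who lost implants before the 12-month follow-up". Inclusion Criteria, item 5, admits "Patients for whom radiographic bone loss, mobility, and prosthetic complications data were recorded and evaluated", and Exclusion Criteria, item 8, removes "Patients with missing data on radiographic bone loss, mobility, prosthetic complications, or implant dimensions".
- **Measurement.** Under Evaluation of Implant Success and Survival: "The success and survival of the implants were evaluated based on the 2007 consensus criteria" of the ICOI, with the data sorted "into four groups: Healthy-Successful, Sufficient Survival, Compromised Survival, and Unhealthy-Failed". Under Evaluation of Radiographic Bone Loss, bone loss is obtained by "subtracting the values obtained immediately after prosthetic loading from those at the 12-month follow-up".
- **Analysed set.** 100 participants. Patients entered once 12 months had passed since delivery, and the sample closed when 100 was reached.

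**The concern.** The period over which implant loss should be counted is the period in which loss makes a patient ineligible. A survival rate from this set would describe the eligibility rules and not the fate of loaded implants. A reader who sees a rate at or near 100% in 100 patients would take it as evidence of good performance, and would take the absence of factor effects on survival as evidence that the factors do not matter. Neither reading would be supported.

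The same condition reaches the rest of the outcome less severely. ICOI grades and complications are observed only in patients who kept their implants, and the plan never says that the results are conditional in this way.

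**Working it through.** The plan states no survival figure to reproduce. The check asks which patients can enter the analysis and what a survival result from them can show.

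**1. Inputs.** Analysed number 100 (Analysis Population Information); loss before the 12-month visit excludes the patient (Exclusion Criteria, item 10); chi-squared for the primary outcome (Statistical Test of Hypothesis); Fisher-Freeman-Halton exact test for qualitative comparisons (Statistical Analysis).

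**2. Can a loss enter?** Item 10 alone keeps out every patient with an earlier loss. Inclusion 5 and exclusion 8 probably act in the same direction. They do not name implant loss, but they require bone-loss and mobility data, and bone loss needs a 12-month value that a lost implant cannot supply. Because the sample was filled to 100, any patient screened out for loss is replaced and leaves no trace in the denominator. Pre-assignment Details lists examples of reasons for exclusion without numbers and does not mention implant loss. Adverse events were not assessed. Observed losses are therefore 0, and survival as implant in place is 100/100.

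**3. What 100/100 would appear to show.** The exact (Clopper-Pearson) 95% interval for 100/100 has lower limit 0.025^(1/100) = 0.9638 and upper limit 1. The implied upper limit on the loss rate is 1 − 0.9638 = 0.0362, or 3.6%.

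That interval assumes that the chance of 100/100 at loss rate q is (1 − q)^100. Under item 10 the chance is 1 for every q:

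| Assumed true loss rate q | Chance of 100/100 if losses could enter, (1 − q)^100 | Chance under item 10 |
|---|---|---|
| 1% | 0.366 | 1 |
| 3% | 0.048 | 1 |
| 5% | 0.006 | 1 |
| 10% | 0.00003 | 1 |

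A result that is certain at every q cannot discriminate between values of q, so the interval carries no information.

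**4. Factor effects on loss.** For a two-level factor against lost or in place, the expected count in each lost cell is row total × 0/100 = 0. The term (O − E)²/E becomes 0/0, so chi-squared is undefined. This was checked at splits of 10/90, 25/75 and 50/50. Fisher's exact test on the 50/50 table gives p = 1.0, and the same follows for any factor because only one table is possible.

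**5. What could be hidden.** The documents give no number of losses, so the counts below are assumptions. With L losses behind 100 retained patients, survival would be 100/(100 + L):

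| L | Survival | Exact 95% interval |
|---|---|---|
| 1 | 100/101 = 99.0% | 94.6% to 100.0% |
| 3 | 100/103 = 97.1% | 91.7% to 99.4% |
| 5 | 100/105 = 95.2% | 89.2% to 98.4% |
| 10 | 100/110 = 90.9% | 83.9% to 95.6% |

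Every row would be reported as 100/100 under the present rules.

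**6. Survival by ICOI group.** A retained implant can fall into any of the four groups, so the grading can vary and be tested. It has no lost implants in it, and the plan does not say which groups count as surviving when a rate is formed.

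**The case against.** The strongest reply is that the plan's only operational definition of survival is the four-group ICOI grading, which is not forced to a single value. On that reading 100/100 belongs to an analysis that the plan never sets out, and no confidence interval is planned either. This is right as far as it goes: the ICOI and complication tests remain valid among retained implants, and the interval in the working shows how the figure would be read, not something the plan promises. It does not rescue a survival rate. The outcome and the intended inference both speak of one, no rule turns the groups into a rate, and lost implants are absent from every group.

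Other points carry some weight:

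- The Statistical Analysis section names an exact test, which does not break down on an empty column. It returns p = 1, which is equally uninformative.
- The ICOI criteria are not reproduced in the documents, so how a lost implant would be graded cannot be confirmed from them. The point needs only that lost implants were never graded.
- Item 10 says before the follow-up, so a loss at the visit itself is not literally covered. The 100 are patients, with implants per patient not stated. Neither restores information on earlier losses.
- The study title concerns complications and bone resorption, and a bone-change measure reasonably requires a retained implant. That supports restricting the bone-loss analysis. It does not support calling survival a primary outcome in the same set.

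**Conclusion.** The concern holds and must be fixed. Item 10 is sufficient on its own; inclusion 5 and exclusion 8 are supporting and only probable. Survival as implant in place is 100/100 by eligibility, gives no information on the loss rate, and allows no test of any factor. The conclusion assumes no loss rate and does not depend on the sample-size calculation.

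ICOI status and complications remain analysable, but apply only to implants in place at 12 months. Whether, and in which direction, that condition biases them cannot be determined from the documents.

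**What to change.** - Rename the primary outcome as ICOI status and prosthetic complications among implants in place at 12 months.
- Do not report a 12-month implant survival rate or a factor effect on implant loss.
- Keep the factor tests on ICOI status and complications, described as conditional on the implant being in place.
- State that losses before 12 months were excluded. Report their number if the archive gives it, including any recorded as missing data under exclusion 8.
- State that the share graded Unhealthy-Failed among retained implants is not one minus a survival rate.

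The cost is mainly wording plus an archive check. The study gives up its survival-rate claim, and no analysis of ICOI status, complications or bone loss changes.

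If survival is to stay in the outcome, the alternative is to admit patients who lost an implant after loading and count them as failures. Item 10 would have to be removed, and inclusion 5 and exclusion 8 relaxed for that outcome. It costs more and depends on the archive identifying those patients.

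### Item 12 mixes retention mode with abutment component and no other item records retention, so complication rates by abutment type are mixed with retention and the crowns at risk of cementation loss cannot be identified

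*Combined protocol and SAP*

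**What the plan says.** Under Data Collection, B. Clinical Parameters, item 12 is "Type of abutment (Standard, Screw-Retained, Ti-Base". The three levels are not defined, and there is no rule for a crown that fits more than one. Two later items are complications connected with retention: item 16, "Presence and history of screw loosening (Yes/No", and item 17, "Presence and history of cementation loss (Yes/No". Both are scored for every crown, with no level for not applicable. Item 18 (chipping) is the third mechanical complication listed. None of the 18 items is a field for screw or cement retention.

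The Outcome Measure Data entry gives the purpose of these fields: "The effect of prosthetic, anatomical and surgical parameters on implant survival rate and prosthetic complications". For categorical comparisons, the Statistical Analysis section says that "the Fisher-Freeman-Halton Exact Chi-Square test was employed for qualitative data comparisons".

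Item 13 begins "Status of the opposing arch (Natural Tooth, Tooth-Supported Fixed Prosthesis, Implant-Supported Fixed Prosthesis" and ends with "Tooth-Supported Removable Partial Prosthesis/Full Denture". It does not say whether the code describes the whole arch or the tooth or restoration that meets the implant crown.

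**The concern.** A categorical factor should answer one question. Item 12 appears to answer two: how the crown is held, and what it sits on. If both kinds of retention occur on a Ti-base, the Ti-Base row is a blend of screwed and cemented crowns in an unknown proportion. The Standard row may be a blend too, since that level is also undefined.

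Two of the three listed mechanical complications are tied to retention, and the prosthetic complication rate is part of the primary outcome. Two things are at stake:

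- A difference between abutment types could come from the component, from retention, or from where the coder placed an ambiguous crown. The data would not tell these apart.
- The cementation loss rate has no proper denominator. A No for a crown that was never cemented counts the same as a No for a cemented crown that held. This affects the descriptive rate as well as any test.

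**Working it through.** The documents give no figure that bears on this point, so there is nothing of theirs to reproduce. The finding comes from reading the items together; the arithmetic below only illustrates it.

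**Step 1. Read the items side by side.**

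| Item | What it records | Retention recoverable? |
|---|---|---|
| 12 | Standard, Screw-Retained, Ti-Base | Only for crowns coded Screw-Retained, if that label means retention |
| 16 | Screw loosening, Yes/No, all crowns | No |
| 17 | Cementation loss, Yes/No, all crowns | Only where the answer is Yes |
| 1–11, 13–15, 18 | Other clinical, implant and prosthetic features | No |

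For a crown coded Ti-Base or Standard with No to cementation loss, nothing on the list says whether it was cemented.

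**Step 2. Denominator of cementation loss.** Let *s* be the screwed share. Assume a loss rate of 10% in cemented crowns and 0% in screwed crowns. The rate over all crowns is 0.10 × (1 − *s*):

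- *s* = 0: 10%
- *s* = 0.5: 5%
- *s* = 1: 0%

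The rate among cemented crowns is 10% whenever there are any. The reported rate moves with *s*, which is not recorded.

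**Step 3. Abutment contrast with no true component effect.** Assume screw loosening of 12% in screwed and 4% in cemented crowns, and assume that all Standard crowns are cemented. The Ti-Base rate is 0.04 × (1 − *s*) + 0.12 × *s*, where *s* is now the screwed share among Ti-base crowns:

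- *s* = 0: 4%, ratio to Standard 4/4 = 1.0
- *s* = 0.5: 8%, ratio 8/4 = 2.0
- *s* = 1: 12%, ratio 12/4 = 3.0

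This is confounding by an unrecorded factor. The top ratio is simply the assumed 12% divided by the assumed 4%, so it shows the mechanism and does not estimate the bias.

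**Step 4. Miscoding, a separate mechanism.** Assume two groups of 50 crowns with true rates of 5% and 20%, and a share *m* of each coded into the other. The observed difference is (20 − 5) × (1 − 2*m*) points:

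| *m* | Observed difference (points) | Approximate power, two-sided 0.05 |
|---|---|---|
| 0% | 15 | 62% |
| 10% | 12 | 44% |
| 20% | 9 | 27% |
| 30% | 6 | 15% |

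The documents give no value for *m*, and it may be zero.

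**Step 5. Would a spurious difference be declared significant?** Usually not. With the rates of Step 3 at *s* = 1 (4% against 12%), the chance that a two-sided Fisher exact test gives p < 0.05 is about 7% with 33 crowns per group and about 17% with 50. For cementation loss of 10% against 0% it is about 11% and 38%. The group sizes are assumptions; the documents give only the total of 100 patients.

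**The case against.** The strongest reply is that the overlap is not in the text. The item is headed as a type of abutment, so the levels may be three mutually exclusive types in local use. No section says that Ti-base crowns were both screwed and cemented in this clinic, or that any crown was coded two ways. This stands as a limit: a reader might infer that double coding occurred, and the documents do not show it. It does not remove the point, because the labels are undefined and retention is recorded nowhere else.

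Second, no comparison by retention is named as an objective. That is true, but the plan does relate prosthetic parameters to complications, abutment type is one of them, and the cementation loss rate needs its denominator whatever is tested.

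Third, false significance would be uncommon with 100 patients. Step 5 bears this out. Low power makes a false declaration less likely; it does not make the reported rates interpretable.

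Fourth, a reader might infer that item 13 has overlapping levels as well. Its first level is a single natural tooth, and each patient has a single-unit crown. Read as the direct antagonist, the five levels are essentially distinct. They overlap only if a mixed whole arch is coded, which the documents do not say. The last level pools partial and full dentures, but pooling is not overlap. Item 13 also has no bearing on retention.

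**Conclusion.** The point holds for item 12. One undefined variable mixes retention mode with abutment component, and no other item records retention. Provided that Ti-base crowns can be screwed or cemented, which is general technical knowledge and not a statement in the documents, two consequences follow: comparisons of complications by abutment type are mixed with retention, and the crowns at risk under item 17 cannot be identified.

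The size cannot be derived from the documents. A reader might take from Step 3 that a spurious effect of up to threefold is to be expected. That is not supported: the ratio restates the assumed rates, and the retention mix is unknown. The defect weakens part of the primary outcome analysis and can be repaired before reporting; it does not invalidate the study. For item 13 the documents support only a secondary clarification of the coding unit.

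**What to change.** Return to the existing charts and replace item 12 with two fields, each with defined levels:

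- abutment component: stock, Ti-base, other;
- retention: screw-retained, cemented.

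Report cementation loss among cemented crowns only, and mark the item not applicable for the rest. Show screw loosening by retention. Present component comparisons within each retention type as descriptive. Report how many charts do not give retention.

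For item 13, add one sentence saying that the code refers to the antagonist contacting the implant crown.

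The cost is one extra chart field for 100 patients. Retention may be missing in some charts, which the documents do not allow one to judge beforehand. Dividing the patients by retention and component makes the cells smaller, which is why the within-retention comparisons should not carry formal conclusions.

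### Occlusal table size (item 14) has no rule for anterior crowns, so its unadjusted comparison may be confounded with anterior versus posterior position

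*Combined protocol and SAP*

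**What the plan says.** Four places in the combined protocol and SAP bear on this.

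- **The factor.** Data Collection, B. Clinical Parameters, item 14 reads "Occlusal table dimensions (Normal/Reduced by 30-40" (per cent). There is no 'not applicable' level and no level for a smaller or larger reduction.
- **The sites in scope.** Item 11 of the same list reads "Anatomical location of the implant (Maxillary Anterior/Posterior, Mandibular Anterior/Posterior". No inclusion or exclusion criterion limits the study to posterior implants, and nothing limits item 14 to posterior crowns.
- **The use of the factor.** The Outcome Measure Data entry is "The effect of prosthetic, anatomical and surgical parameters on implant survival rate and prosthetic complications". Item 14 is therefore one of the factors whose effect is to be reported.
- **The tests.** Under Statistical Analysis, "the Fisher-Freeman-Halton Exact Chi-Square test was employed for qualitative data comparisons" and "The Mann-Whitney U test was used for pairwise comparisons". The Kruskal-Wallis test with Dunn's test is the only other comparison named. None of these is stratified by, or adjusted for, implant location.

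Exclusion criterion 8 removes "Patients with missing data on radiographic bone loss, mobility, prosthetic complications, or implant dimensions". Occlusal table is not on that list.

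**The concern.** An occlusal table is a feature of posterior teeth; incisors and canines have an incisal edge or a cusp tip. This is general anatomy and not a statement in the documents. Someone scoring an anterior crown under item 14 has two codes to choose from. 'Normal' is the likelier choice, because there is no table to reduce.

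If that is what happens, 'Reduced' contains posterior crowns only and 'Normal' contains posterior and anterior crowns together. Any difference in complication risk between regions then enters the 'Normal' versus 'Reduced' comparison. It can create an apparent effect of table size or hide a real one. A larger sample would not remove it.

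A smaller gap lies in the levels themselves. The plan does not say how a crown reduced by less than 30% or more than 40% would be coded.

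**Working it through.** The plan gives no figure for this comparison, so there is nothing of its own to reproduce. What follows shows how large the distortion could be.

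**Input from the documents:** 100 participants analysed (Analysis Population Information).

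**Assumptions, none of them in the documents:** one crown per participant; A anterior crowns, with A = 10, 25 or 40; all anterior crowns coded 'Normal'; posterior crowns split 60:40 between 'Normal' and 'Reduced'; posterior complication risk 15% when table size has no effect; anterior risk 5%, 15% or 25%.

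**Formula.** With n posterior 'Normal' crowns at risk p and A anterior crowns at risk a:

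pooled 'Normal' risk = (n × p + A × a) / (n + A)

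apparent risk ratio = risk in 'Reduced' / pooled 'Normal' risk

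**No true effect (15% in both posterior groups; the correct ratio is 1.00)**

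| A | n 'Normal' posterior / 'Reduced' | Anterior risk 5% | Anterior risk 15% | Anterior risk 25% |
|---|---|---|---|---|
| 10 | 54 / 36 | (8.1 + 0.5)/64 = 0.134; ratio 1.12 | 1.00 | (8.1 + 2.5)/64 = 0.166; ratio 0.91 |
| 25 | 45 / 30 | (6.75 + 1.25)/70 = 0.114; ratio 1.31 | 1.00 | (6.75 + 6.25)/70 = 0.186; ratio 0.81 |
| 40 | 36 / 24 | (5.4 + 2.0)/76 = 0.097; ratio 1.54 | 1.00 | (5.4 + 10.0)/76 = 0.203; ratio 0.74 |

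**A true effect (20% in 'Normal' and 12% in 'Reduced' posterior crowns, ratio 0.60; anterior risk 5%)**

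- A = 10: (10.8 + 0.5)/64 = 0.177, apparent ratio 0.68
- A = 25: (9.0 + 1.25)/70 = 0.146, apparent ratio 0.82
- A = 40: (7.2 + 2.0)/76 = 0.121, apparent ratio 0.99

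**Effect on the test.** A second illustration used a 50:50 posterior split, risks of 5% anterior and 20% posterior, no true effect, and 1,500 simulated Fisher exact tests per setting at the plan's 0.05 level.

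| Anterior crowns | Anterior share of 'Normal' | False difference, 'Reduced' minus 'Normal' | Rejection rate |
|---|---|---|---|
| 5 | 10% | 1.4 points | about 4% |
| 10 | 18% | 2.7 points | about 4% |
| 20 | 33% | 5.0 points | about 7% |
| 30 | 46% | 6.9 points | about 12% |
| 40 | 57% | 8.6 points | about 15% |

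With equal regional risks (15% and 15%) the rejection rate was about 3 to 4%. Coding all anterior crowns 'Reduced' instead of 'Normal' reverses the sign of the false difference.

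**Posterior crowns only.** Under the same assumptions the null case gives 0.15/0.15 = 1.00 and the true-effect case gives 0.12/0.20 = 0.60, whatever A is.

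**The case against.** The bias is not demonstrated. It needs three things together: a fair number of anterior crowns, coded mostly into one level, with a risk that differs from the posterior risk. The documents establish none of them. The parameter list is introduced only by "The parameters assessed during these appointments include", which does not say that every item was scored for every crown. Because exclusion criterion 8 does not name occlusal table, an anterior crown could be left blank on item 14, stay in the study, and drop out of this one comparison. The list is also terse elsewhere: item 18 (framework-ceramic separation) has no 'not applicable' level although item 15 includes monolithic crowns. A missing level in the list does not prove that none was used. With 5 to 10 anterior crowns the false difference stays below 3 points, and with equal risks it is nil.

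All of this stands, and it limits the point to what may happen. It does not close the gap, because the plan does not tell the reader which situation applies.

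Other factors linked to location, such as material, abutment or diameter, could also be confounded under unadjusted tests. That is true. What sets item 14 apart is that the factor may not be defined at anterior sites. If no anterior crown can be 'Reduced', the anterior stratum says nothing about table size, and restriction is the direct remedy.

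On the levels, a reader might infer that crowns reduced by some other amount were misclassified. Nothing in the documents shows that such crowns existed; the 30-40% band may simply describe what was done.

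**Conclusion.** The point holds as a conditional one. Item 14 has no rule for anterior crowns, anterior implants are in scope, and no planned analysis separates table size from location, so the comparison may be confounded with position.

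On the assumed inputs, a null effect could appear as a risk ratio anywhere from 0.74 to 1.54, and a true ratio of 0.60 could appear as 0.68 to 0.99. The direction depends on which region carries the higher risk, and the bias vanishes if the risks are equal. That anterior crowns have no occlusal table is itself an assumption from general anatomy.

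A reader might go further and infer that the comparison does partly measure anterior versus posterior position, or that anterior crowns can only have been coded 'Normal'. The documents support neither: they do not report how anterior crowns were coded, how many there were, or risk by region.

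The point affects one explanatory factor among many and not the study as a whole. It still merits a change of method, because the remedy is specific and cheap.

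**What to change.** 1. State in the SAP that item 14 is not applicable for the two anterior levels of item 11, and restrict every item 14 comparison (complications, bone loss, ICOI group) to posterior crowns. Report how many crowns this leaves.
2. State how reductions outside 30-40% were coded. Where records allow, compare 'not reduced' with 'reduced'. This should not require the percentage reduction to be measured again: as listed, item 14 holds a two-level code, and no unreduced reference size is recorded.

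The first change uses item 11, which is already held, and needs one SAP sentence. The second needs a sentence and perhaps a check of records. The downside is a smaller denominator for this factor: 60 to 90 crowns instead of 100 if 40 to 10 are anterior. If the anatomical assumption is right, the crowns set aside carry no information about table size.
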